4.14 Evaluation Methods**Photographs:**

Photographs will be taken at all visits and will be used to assess safety and efficacy of treatment.

Treatment Discomfort/Pain Evaluation:

Subjects will be asked to report the general level of treatment discomfort on a scale of 0 (none) to 10 (maximum intolerable pain) using the universal pain assessment tool (Appendix B)

Subject Experience Evaluation:

Subjects will be asked to complete a questionnaire to assess their treatment experience.

User Experience Evaluation:

The clinician will be asked to complete a questionnaire to assess the usability of the device.

Diary:

A subject diary may be collected to assess the recovery time of the treatment for 7 days post treatment.

Subject Satisfaction:

The subject will be asked their level of satisfaction using a 6-point Likert scale that ranges from “extremely satisfied” to “extremely unsatisfied.”

Rating	Description
6	Extremely Satisfied
5	Satisfied
4	Slightly Satisfied
3	Slightly Unsatisfied
2	Dissatisfied
1	Extremely Unsatisfied

Ultrasound (U/S):

An ultrasound scan is a medical test that uses sound waves to capture live images from the inside of the body. The subject will most likely be lying down on a table with a section of their body exposed for the test. A special lubricating jelly will be applied to their skin. This prevents friction between the ultrasound transducer—similar in appearance to a microphone—and the skin. The jelly also helps transmit the sound waves. After the procedure, the gel will be cleaned off the subject. The whole procedure typically lasts less than 30 minutes. Following it, the subject will be free to go about their day and normal activities.

Optical Coherence Tomography (OCT)

An OCT device uses a very low power laser that is directed at the skin. The reflected light is captured by the device to provide images of the skin layer down to 1 millimeter depth. It may be used to help evaluate the effect of RF exposure on the skin. The subject will be asked to lay down and the device’s arm will be brought into contact with the skin area of interest. Depending on the area of skin to be measured, the exam will take 15 to 30 minutes to perform.

4.15 Adverse Event Assessment

Recording of adverse events will take place at all visits.

4.16 Adverse Event Recording

All data captured must be supported by the Investigator's timely assessment and documentation of the event in the case report forms or source documents. All documented adverse events will be reviewed by the Sponsor or designee to determine whether the adverse event meets regulatory reporting requirements and to ensure timely adverse event reporting to meet local and global regulatory requirements.

Adverse Events Pertaining to the Radiofrequency Device:

Mild discomfort during treatment may be experienced by the subject. Typically, the discomfort is temporary and localized within the treatment area. Mild edema (swelling) and erythema (redness) may occur. Initial studies indicate that these side effects typically resolve within 2 to 24 hours.

Other anticipated side effects may include; pain, skin burns, bleeding, scarring, crusting, bruising, infection, itching, prolonged edema (swelling), and erythema (redness), hardness, and nodules. Loss of hair pigment may also occur within and adjacent to the treatment area.

Adverse Events Pertaining to Surgical Marker:

Using surgical marker has minimal risks and may produce effects on the body such as redness or a rash. Markings may remain visible for a few days or may be removed with alcohol.

Adverse Events Pertaining to Gel:

The gel is a water-based gel that may be placed on the skin during an RF treatment. No known adverse events are documented. However, an allergic reaction is always possible when placing a topical gel onto the skin. Allergic reaction may include a mild reaction such as skin redness, irritation or hives.

Eye injury due to direct ocular Radiofrequency exposure may occur:

Corneal Eye Shields (sterile, plastic, non-conductive) must be used for any radiofrequency surgical procedure being performed over the globe of the eye.

Adverse Events Pertaining to Cooling:

Anticipated transient side effects associated with cooling may include tingling, itching, decreased sensation, numbness, redness and pain.

Adverse Events Pertaining to Anesthetic:

1% lidocaine (Lidocaine) with Epinephrine Injection

Pain and numbness may be experienced at the site of the injection. Redness, rash, infection, skin damage or nerve damage at the site of the injection may also be experienced. Temporary loss of sensation and muscle function at the site of injection may be experienced. Lidocaine with epinephrine contains the preservative sodium metabisulfite which may cause allergic-type reactions or intolerances including anaphylactic symptoms such as itching, hives, swollen areas of the body, and/or trouble breathing and life-

threatening or less severe asthmatic episodes in certain susceptible people.

Adverse Events Pertaining to Nitronox:

May experience nausea, vomiting, excessive sweating, euphoria, excitement, deep sedation, drowsiness, sleep, dizziness, lightheadedness, dysphoria, amnesia, and headaches.

Adverse Events Pertaining to Ultrasound:

Ultrasound imaging has minimal risks and may produce effects on the body such as redness and pockets of gas. Skin rashes from use of the ultrasound gel may also occur.

Other Anticipated Adverse Events:

Incomplete response or no response is relatively common since some subjects may not respond to treatment.

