4.0 PROTOCOL

4.1 Purpose and Objectives

The purpose of this study is to develop parameters and assess the safety of the radiofrequency device for a variety of treatments. Treatment results may also be evaluated.

The Primary Objectives are:

- To develop treatment parameters.
- Assess the safety through recording of side effects during course of study.

The Secondary Objectives are:

- Subject satisfaction via continuous verbal feedback during the procedure and at follow up visits.
- Assess the ease of use, patient response, treatment time, functions of the new device.

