4.8 Treatment

- Radiofrequency Device Treatment:
 - The type of treatment will determine if gel should be applied to the skin prior to treatment. The gel is a conductive gel created for treatments that use radio frequency (RF) to ensure the proper connection between the hand piece and the skin.
 - A neutral pad will be used in accordance with the operator's manual for the device.
 - The hand piece, applicator or tip will be placed in contact with the skin.
 - The entire defined treatment area will then be treated by delivering energy to the skin.
 - The hand piece, number of passes and parameters used for the treatment will be determined by the Investigator.
 - Parameters may be adjusted throughout the treatment to increase subject comfort.
 - Contact cooling built into the 60mm handpiece may be used to increase subject comfort.
 - Nitronox may be used to increase subject comfort and will be determined by the Investigator.
- Procedural adverse events will be documented.
- Subjects will be asked to report the general level of treatment discomfort/pain on a scale of 0 (none) to 10 (maximum intolerable pain).
- Some subjects may have an incomplete response or no response by the end of the study. At the end of the study treatments using an FDA approved/cleared treatment method may be discussed with the subject and obtained at the cost of the subject.

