9.0 ADVERSE REACTIONS DEFINITIONS AND REPORTING REQUIREMENTS

All adverse events that occur, starting from the time of the first treatment, will be recorded in the source documents.

Adverse Events occurring will be captured and followed until the condition resolves, stabilizes, is otherwise explained, or the subject is lost to follow-up. Subjects will be instructed that they may contact the Investigator at any time throughout the course of the study.

The Investigator and/or designated study staff will review each event and assess its relationship to the study device (not related, unlikely, possible, probable, and highly probable). The following definitions will be used for rating relationship to the device treatments:

- Not related – The event is clearly related to other factors such as the subject’s clinical state, therapeutic interventions, or concomitant medications administered to the subject.
- Unlikely – The event was most likely produced by other factors such as the subject’s clinical state, therapeutic interventions, or a concomitant medication administered to the subject; and does not follow a known response pattern to the investigational product.
- Possible – The event follows a reasonable temporal sequence from the time of investigational product administration; **and/or** follows a known response pattern to the study sampling sessions; **but** could have been produced by other factors such as the subject’s clinical state, therapeutic interventions, or concomitant medications administered to the subject.
- Probable – The event follows a reasonable temporal sequence from the time of investigational product administration; **and** follows a known response pattern to the investigational product; **and** cannot be reasonably explained by other factors such as the subject’s clinical state, therapeutic interventions, or concomitant medications administered to the subject.

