16.0 DATA ANALYSIS

All data will be analyzed at the end of the study. The primary analysis will be performed by the intention-to-treat approach. All subjects who begin the treatment is considered to be part of the study whether the subject completes the study or not. Additional per-protocol analysis may also be performed on subjects who complete the entire clinical trial according to the protocol. The most appropriate method of handling missing values will be chosen based on the particular trial's goals, endpoints and context.

Endpoints will be summarized with descriptive statistics. Continuous variables will be summarized with n, mean, standard deviation and range. Frequency counts and percentage of subjects within each category will be presented for categorical data. If applicable, Student's t-test may be used to determine if two sets of data are significantly different from each other and p-values will be reported. If the calculated p-value is below the threshold chosen for statistical significance (0.05, or 0.01 level) then the null hypothesis is rejected in favor of the alternative hypothesis. Subgroup analyses may be performed to identify a subject population that achieves the most benefit. Interim results may also be collected and reported as deemed necessary.

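### Section 4.16 lists incomplete or no response as an anticipated adverse event, and nothing in the plan keeps it out of a reported adverse event incidence

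*Combined protocol and SAP*

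**What the plan says.** Section 4.16, on adverse event recording, sets out anticipated effects by source: the device, the marker, the gel, cooling, anesthetic, Nitronox and ultrasound. Its last block is headed "Other Anticipated Adverse Events" and contains one sentence: "Incomplete response or no response is relatively common since some subjects may not respond to treatment".

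Section 4.8, on treatment, covers the same outcome in a different role: "Some subjects may have an incomplete response or no response by the end of the study". That sentence stands apart from the bullet on documenting procedural adverse events.

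Section 4.1 makes safety a primary objective: "Assess the safety through recording of side effects during course of study". Section 4.15 has adverse events recorded at every visit. Section 9.0 sets the capture rule: "All adverse events that occur, starting from the time of the first treatment, will be recorded in the source documents". It then requires each event to be rated for relationship to the device on five levels and for severity on three. Follow-up is governed by this sentence: "Adverse Events occurring will be captured and followed until the condition resolves, stabilizes, is otherwise explained, or the subject is lost to follow-up".

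Section 16.0 plans descriptive statistics only. For categorical variables, "Frequency counts and percentage of subjects within each category will be presented for categorical data".

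**The concern.** Failing to respond to a cosmetic or heating treatment is an efficacy outcome. Section 4.16 nevertheless places it among the adverse events, and Section 9.0 tells sites to record every adverse event. A site that looks for a rule on what counts finds no general definition in Section 9.0, only the lists in Section 4.16, and non-response is on them.

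Safety is one of the study's two primary objectives. If non-response is logged and later included in a percentage of subjects with any adverse event, that percentage no longer describes harm. The protocol itself expects non-response to be relatively common, so the distortion need not be small. There is also no response criterion, so sites that did log it would have no shared rule for when it had occurred.

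**Working it through.** The documents state no adverse event rate, non-response rate or safety endpoint, so there is no figure of the plan's own to reproduce. The check is first textual and then an illustration of possible size.

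**Text, side by side**

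1. Classification. Section 4.16 puts non-response under an adverse event heading; Section 4.8 presents it as a result of treatment. One outcome is classed in two ways.
2. Capture. Sections 4.15 and 9.0 require all adverse events to be recorded. Section 9.0 defines serious adverse events and gives the rating scales, but no general definition of an adverse event and no exclusion for lack of effect. Nothing there overrides Section 4.16.
3. Grading. The severity scale in Section 9.0 rests on discomfort and interference with daily activities. The higher relationship categories rest on timing after treatment and a known reaction pattern. Neither scale can sensibly grade the absence of an effect.
4. Reporting. Section 16.0 names no adverse event incidence, numerator or time window. It therefore neither directs that non-response be counted nor prevents it.

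**Possible size (assumed rates)**

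Let p be the share of subjects with a true side effect and q the share of non-responders. Neither is in the documents. If non-response is counted as an event and the two are independent, the share with at least one event is

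1 − (1 − p)(1 − q).

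Without independence, the share lies between max(p, q) and min(1, p + q).

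| p | q | Calculation | Share with an event | Range without independence |
|---|---|---|---|---|
| 10% | 10% | 1 − 0.90 × 0.90 | 19% | 10% to 20% |
| 10% | 20% | 1 − 0.90 × 0.80 | 28% | 20% to 30% |
| 10% | 30% | 1 − 0.90 × 0.70 | 37% | 30% to 40% |
| 40% | 10% | 1 − 0.60 × 0.90 | 46% | 40% to 50% |
| 40% | 20% | 1 − 0.60 × 0.80 | 52% | 40% to 60% |
| 40% | 30% | 1 − 0.60 × 0.70 | 58% | 40% to 70% |

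Relative to p, the independent case multiplies the rate by 1.9 to 3.7 when p is 10% (19/10 to 37/10) and by 1.15 to 1.45 when p is 40% (46/40 to 58/40). If all 225 subjects allowed by Section 4.2 were treated, p = 10% and q = 20% would turn 22.5 expected subjects with an event (225 × 0.10) into 63 (225 × 0.28).

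**The case against.** The strongest reply is that this is a misplaced sentence in a risk list, with no rule behind it. After its opening paragraph, Section 4.16 describes anticipated risks; it also contains an eye-shield precaution and a remark that no adverse events are known for the gel. The primary objective speaks of side effects, a term that Section 4.16 applies to bodily effects and never to non-response. Sections 4.2 and 4.10 name side-effect and efficacy assessments separately. The sponsor or its designee reviews every documented event, and a table by category could show non-response on its own identifiable line. The study is open label with no planned safety test to distort.

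Much of this stands, and it limits the point in four ways:

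- A reader might infer that the plan's primary safety rate counts lack of efficacy as harm. No such rate is written, and no sentence directs that non-response enter a safety count.
- A reader might infer that a non-responder must be followed without end. The follow-up rule also allows an event to close when it stabilizes or is otherwise explained, and Section 9.0 accepts an unchanged outcome.
- A reader might infer that centers will record non-response differently. With 8 centers this is a risk; nothing in the documents shows that it happens.
- A reader might infer that side-effect records are the only safety measure. Section 4.14 also uses photographs to assess safety.

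What does not stand is the idea that existing wording already settles the matter. The sponsor's review in Section 4.16 concerns regulatory reporting, not reclassification of efficacy outcomes. Separate naming of side effects elsewhere does not cancel an explicit adverse event heading in the section on adverse event recording.

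**Conclusion.** The point holds as a stated misclassification. Section 4.16 calls non-response an anticipated adverse event, Section 4.8 treats it as a treatment outcome, and Section 9.0 requires adverse events to be recorded and graded without a definition or exclusion that would resolve the conflict. A site following the text literally would record an efficacy outcome as safety data, and an any-event incidence could then mix the two.

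The conclusion goes no further than that. The documents do not show that non-response will be counted, and they do not fix how much it would matter. The figures of 19% to 37% and 46% to 58% rest wholly on assumed side-effect rates of 10% and 40%, assumed non-response of 10% to 30%, independence, and every non-responder being logged. The relative effect shrinks as the true side-effect rate rises. The correction is worth making because it is nearly free and protects a primary objective.

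**What to change.** Make two edits.

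1. Move the non-response sentence from Section 4.16 to Section 4.8 and remove the heading that it leaves empty. Keep the statement that non-response is relatively common: Section 4.8 does not say this now, so simple deletion would lose it.
2. Add to Section 9.0 a sentence such as: Incomplete or no response is a treatment result; it is not recorded or graded as an adverse event and is left out of any adverse event incidence.

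Treatments, visits and the recording of actual side effects do not change. The only cost is a small text amendment, which under Section 20.0 needs written approval from the Institutional Review Board.

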5.0 PREGNANCY

Females may not participate in this study if they are pregnant, breastfeeding, were pregnant within the last three months or are planning a pregnancy during the course of the study.

If the subject thinks they have become pregnant during the study it is important that they inform the Investigator immediately. If she becomes pregnant or thinks that she may be pregnant, she will be removed from the study and will be asked to perform a final evaluation similar to that of the final follow-up visit. The Investigator may request to track the pregnancy and will report the pregnancy to the Sponsor.

6.0 SUBJECT WITHDRAWAL

The subject is free to withdraw from this study at any time. The subject must inform the Investigator immediately if they intend to withdraw. To terminate the subject's participation in this study, they must contact the Investigator at the contact information listed on page one of the informed consent form. They will be asked to come to the study clinic or Investigators office to complete a final follow up visit and may be asked to perform end of study procedures. Their decision to participate in this study or to withdraw from this study will not influence the availability of their future medical care and will involve no penalty or loss of benefits to which they are otherwise entitled.

The Investigator in charge of the study can remove the subject from this study without their consent for any reason, including, but not limited to:

- a. His/her judgment that any condition or circumstance may jeopardize their welfare or the integrity of the study.
- b. Their failure to follow the instructions of the Investigator(s).
- c. If the study is stopped by the sponsor and/or Investigators participating in the study prior to completion.

7.0 PHOTOGRAPHY

Standardized photographs may be taken of the treatment area. If photographs are taken of the face the subject will be asked to remove jewelry, make up and lotions prior to each photo session. Photographs will be taken with an appropriate high resolution digital camera. Camera settings (lighting, distance, background, polarization, etc.) will be reproduced at each visit, so that photographs are suitable for comparison.

8.0 RISK ANALYSIS AND MANAGEMENT

The Investigator in this clinical trial has been invited to participate based on his/her previous experience with the use of system, similar systems and industry experience. Experience with treatments is the most critical element in managing subject risk in this trial. All other known risks will be disclosed to the subject via the informed consent process. Since this is an elective procedure and the subjects are volunteers, it can be assumed that their signature on the informed consent is indicative of their agreement to accept the risks involved.

In addition, as with any study, there is a risk of bias. To minimize/avoid bias objective evaluation methods may also be used in conjunction with subjective evaluation methods when feasible.

9.0 ADVERSE REACTIONS DEFINITIONS AND REPORTING REQUIREMENTS

All adverse events that occur, starting from the time of the first treatment, will be recorded in the source documents.

Adverse Events occurring will be captured and followed until the condition resolves, stabilizes, is otherwise explained, or the subject is lost to follow-up. Subjects will be instructed that they may contact the Investigator at any time throughout the course of the study.

The Investigator and/or designated study staff will review each event and assess its relationship to the study device (not related, unlikely, possible, probable, and highly probable). The following definitions will be used for rating relationship to the device treatments:

- Not related – The event is clearly related to other factors such as the subject’s clinical state, therapeutic interventions, or concomitant medications administered to the subject.
- Unlikely – The event was most likely produced by other factors such as the subject’s clinical state, therapeutic interventions, or a concomitant medication administered to the subject; and does not follow a known response pattern to the investigational product.
- Possible – The event follows a reasonable temporal sequence from the time of investigational product administration; **and/or** follows a known response pattern to the study sampling sessions; **but** could have been produced by other factors such as the subject’s clinical state, therapeutic interventions, or concomitant medications administered to the subject.
- Probable – The event follows a reasonable temporal sequence from the time of investigational product administration; **and** follows a known response pattern to the investigational product; **and** cannot be reasonably explained by other factors such as the subject’s clinical state, therapeutic interventions, or concomitant medications administered to the subject.
- Highly Probable – The event follows a reasonable temporal sequence from the time of investigational product administration; **and** follows a known response pattern to the investigational product; **and** cannot be reasonably explained by other factors such as the subject’s clinical state, therapeutic interventions, or concomitant medications administered to the subject; **and** either occurs immediately following investigational product administration, **or** improves on stopping the investigational product, **or** reappears on repeat exposure, **or** there is a positive reaction at the application site.

Each adverse event reported will be graded on a 3-point severity. Using the following definitions for rating severity will be used:

- Mild – easily tolerated, causing minimal discomfort, and not interfering with normal everyday activities.
- Moderate – sufficiently discomforting and may interfere with normal everyday activities.
- Severe – incapacitating and/or preventing normal everyday activities.

A Serious Adverse Event (SAE) is any adverse device experience that results in any of the following outcomes: death, a life-threatening adverse device experience, in-patient hospitalization or prolongation of hospitalization, a persistent or significant disability/incapacity, or a congenital anomaly/birth defect. Important medical events that may or may not result in death, be life-threatening, or require hospitalization may be considered a serious adverse device experience when, based upon appropriate medical judgment, they may jeopardize the subject or subject may require medical or surgical intervention to prevent one of the outcomes listed in this definition

If any of the above adverse events are serious as defined by the FDA Code of Federal Regulations (CFR), Title 21, special procedures will be followed. All serious adverse events will be reported within 24 hours of acknowledgment to the Sponsor whether or not the serious events are deemed sampling session-related. All serious event reporting will adhere to 21 CFR part 812 and the IRB will be notified accordingly.

The SAE information will be entered into the database and a desk copy of the complete SAE report will be submitted to the files.

Adverse events, whether serious or non-serious, will be followed until the condition is resolved, stabilized, otherwise explained or the subject is lost to follow-up. Adverse events will be captured throughout the study and where appropriate, medical tests and examinations will be performed to document the resolution of event(s). Outcomes may be classified as resolved, improved, unchanged, worse, fatal, unknown or lost to follow-up. Following the resolution of any study-associated adverse events there will be no further adverse event reports for that subject.

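### Section 9 contradicts itself on what counts as a serious adverse event, and its single device-directed causality scale cannot mark a Nitronox or lidocaine reaction as caused by the study session

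*Combined protocol and SAP*

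**What the plan says.** Four parts of the protocol bear on this point.

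- **SAE definition (Section 9.0).** "A Serious Adverse Event (SAE) is any adverse device experience that results in any of the following outcomes". The device wording returns in the life-threatening item of the list. It returns again in the clause on important medical events, which "may be considered a serious adverse device experience when, based upon appropriate medical judgment" they may jeopardize the subject or call for intervention.
- **SAE reporting (Section 9.0, next paragraph).** Special procedures follow if any of the adverse events is serious under Title 21 of the CFR. All SAEs go to the sponsor within 24 hours "whether or not the serious events are deemed sampling session-related".
- **Causality (Section 9.0).** Staff review each event and "assess its relationship to the study device (not related, unlikely, possible, probable, and highly probable"). The next sentence words the target more broadly: "The following definitions will be used for rating relationship to the device treatments". *Not related* begins "The event is clearly related to other factors such as the" and goes on to name the subject's clinical state, therapeutic interventions and concomitant medications.
- **Ancillary agents (Sections 4.8 and 4.16).** Section 4.8 lets the investigator use Nitronox for comfort. Section 4.16 lists its effects, among them "excessive sweating, euphoria, excitement, deep sedation, drowsiness". It also lists harms of 1% lidocaine with epinephrine, including "allergic-type reactions or intolerances including anaphylactic symptoms" and life-threatening asthmatic episodes. Shorter lists cover gel, surgical marker and ultrasound.

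**The concern.** Safety is one of the two primary objectives in Section 4.1, and Section 4.2 plans for 8 centers. Sites therefore need one answer to two questions: is this event serious for reporting purposes, and did taking part in the study cause it?

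On the first, the definition and the reporting rule have different scopes. A site that works from the definition could conclude that a life-threatening reaction to an anesthetic given at a study session is not a device experience and does not start the 24-hour clock. A site that works from the reporting rule would report it.

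On the second, the scale asks only about the device or its treatments. An agent given because of the study session is handled in the same way as an unrelated medication. At stake are uniform expedited reporting and a safety record that can separate effects of the radiofrequency device from effects of what was given alongside it.

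**Working it through.** No arithmetic applies. The check is to take one case through the text: a serious reaction, at a study session, clearly due to Nitronox or to lidocaine with epinephrine.

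**Step 1. Is it an SAE?**

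| Text in Section 9.0 | Scope as worded | Result for the test case |
|---|---|---|
| SAE definition | Adverse device experiences | Not an SAE on a literal reading |
| Important-medical-event clause | Serious adverse device experiences | Same limit |
| Title 21 sentence | Any of the adverse events | Can be serious; triggers special procedures that the sentence does not specify |
| 24-hour sentence | All SAEs, related to a session or not | Depends on which meaning of SAE the site uses |

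The first two rows limit seriousness to device experiences; the last two do not fit that limit. If every SAE were a device experience, a rule covering SAEs unrelated to a session would have little to act on. The 24-hour sentence cannot settle the matter, because it uses the term that the definition has just narrowed. Its qualifier also refers to sampling sessions, which this study does not define. The same phrase appears in the definition of *Possible*.

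**Step 2. How is it rated?**

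- *Not related*: met when other factors are clearly the cause, and therapeutic interventions and concomitant medications count as other factors. Study-administered agents are not excepted. The test case lands here.
- *Unlikely*: needs other factors to be the most likely cause and also no match to a known response pattern of the investigational product.
- *Possible*: available when the timing or pattern fits but other factors could have produced the event. An uncertain drug reaction may therefore be rated *Possible* against the device.
- *Probable* and *Highly Probable*: both require that other factors cannot reasonably explain the event, so one explained by Nitronox or lidocaine cannot reach them.

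A clear drug reaction thus becomes *Not related*, and an uncertain one may be credited to the device. No rating says that the session, rather than the device, caused the event.

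**Step 3. Does anything depend on that missing category?**

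Yes. Section 9.0 ends adverse event reports for a subject once study-associated events have resolved, but does not say which ratings count as study-associated.

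**Step 4. Do all five listed items behave alike?**

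No. Gel, marker and ultrasound have mostly mild listed effects. Gel and marker reactions can reasonably be rated as related, either as part of the device treatments or under the application-site criterion of *Highly Probable*. The point rests on Nitronox and lidocaine with epinephrine.

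**The case against.** The strongest reply is that the protocol works on an all-cause basis in practice. Section 9.0 records all adverse events from the first treatment and follows them to an outcome. Section 4.8 has procedural events documented. Section 4.16 has the sponsor review every documented event against regulatory reporting requirements, with no device limit. The Title 21 test is not worded for device experiences, and the 24-hour rule makes most sense if SAEs of any cause are meant. The sampling wording may be leftover text that does not cancel the intent. The phrase adverse device experience is itself undefined and could be read generously.

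Much of this stands. A reader might infer that serious Nitronox or lidocaine reactions fall outside SAE reporting. The documents do not support that: they contain text pointing each way, which is a contradiction and not a settled exclusion. These events would still be recorded, followed and seen by the sponsor.

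A reader might also infer that the trial will understate a device-related event rate. That does not follow either. Section 4.1 rests safety on recording side effects, and Section 16.0 summarizes endpoints descriptively without naming such a rate or restricting summaries to related events.

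The safeguards do not remove the defect, however. None tells a site that the 24-hour clock starts for a serious event caused by an ancillary agent, and none adds a way to attribute that event to the study session.

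**Conclusion.** The point holds in a limited form. Section 9.0 gives two incompatible scopes for serious events, and its one causality scale classes a reaction clearly due to Nitronox or lidocaine with epinephrine as *Not related*. Two sites could treat the same event differently and each cite the protocol. This follows from the wording alone.

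The practical size is unknown. The documents do not say how many subjects would receive either agent or how often reactions are expected, so no count of affected subjects or missed reports is offered. The conclusion assumes that sites apply the definitions as written; training or form instructions outside these documents could narrow the gap. The change is worth making because safety is a primary objective and the correction is small.

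**What to change.** Amend Section 9.0 as follows.

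1. Define an SAE as any adverse event, whatever its cause, that meets one of the listed outcomes. Carry this through the life-threatening item and the important-medical-event clause, so that the definition agrees with the 24-hour rule.
2. Replace the references to sampling sessions with study treatment or procedure, both in the SAE reporting sentence and in the definition of *Possible*.
3. Keep the device rating and add one field to the adverse event form: relationship to a study procedure or ancillary agent, with the agent named. For that field, do not count study-administered agents as unrelated other factors. Tabulate device-related and procedure- or agent-related events separately.

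The cost is revised wording and one extra field per event, with no added visits or assessments. The total of study-related events may look slightly higher, and the separate tabulation will show why.
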